### **Secondary outcomes (from survey data):**

1. Percent of all surveyed transactions that include an SSB
2. Percent of all surveyed beverage transactions that include an SSB
3. Total calories per surveyed transaction

### **Description of data:**

The first is a longitudinal data set (at the school level) of store purchases from July – August 2019 obtained by trained research assistants in three schools located in Guatemala City. Data are daily purchases of food items and beverages by students. Sample is total purchases obtained from scanning products' barcodes or using an application (Square app) to assign unique codes to products without a barcode. Data include food purchases, brand, flavor, size, and quantity. Additionally, an inventory of beverages' brand, flavor, price, size (mL), serving size (mL) as reported in the Nutrition Facts Panel, calories (kcal), total fat (g), saturated fat (g), total carbohydrates (g), sugar (g), sodium (mg), protein (g), ingredients, total sugar, sodium, and protein per container (g).

The second dataset is an intercept survey conducted with students after they made a purchase at the school store. Data include total expenditure, number and type of items purchased (i.e., beverage, food, or non beverage/food item), perception of healthfulness of

specific beverages (i.e., water, fruit drink, soft drink, light soft drink), and the label awareness, recall, use, and trust. Usual SSB consumption, demographics, height, and weight are also included in the survey.

For our primary analysis, we will look only at the 2 schools which were randomly assigned to condition (one treatment and one control school).

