include 100% juice). Frequencies and percentages will be used to describe categorical variables such as percent of students purchasing a sugary drink. Medians and interquartile ranges will be reported for continuous variables that exhibit skewness. Data will be descriptively summarized overall and by labeling strategy. All outcomes will be analyzed at the purchase level. The mean volume of sugary drinks at each two-week period will be modeled among the calorie label, text label, and graphic label arms by a linear regression model including intervention arm, two-week period, interactions of period and intervention arm and type of school (private or public) as independent variables. We will conduct exploratory analyses to examine whether usual frequency of sugary drink intake (high versus low) and biological sex moderate label effects. Examining only aggregate sales data could lead to incorrect inferences. Therefore, complementary individual-level survey data on purchases will also be collected. This aggregate/individual-level data combination will improve inferences about label effects. Although stratification by school type guarantees this variable will be balanced across our intervention arms, we are including it as a covariate in the model because it will enhance the precision of estimating intervention effects, as it explains variability in the outcome. The effectiveness of the interventions will be tested by evaluating the null hypothesis that the coefficients of the interactions of period and intervention are 0, indicating no change in the difference in volume of sugary beverages purchased across intervention arms from baseline. To account for clustering of purchases within schools, test statistics will be corrected using the variance inflation factor (VIF) as determined by the estimated intraclass correlation coefficient (ICC) for within school correlation. Primary and secondary outcomes in the calorie, text-based warning label, and graphic warning label arms will each be compared to one another. A Bonferroni-holm correction will be applied to control for multiple comparisons. We do not expect substantial missing data due to the point-of-sale technology we are using. The primary analysis will examine changes in labeled (sugary) and non-labeled beverages. Secondary analyses will examine changes for the following specific beverage categories: sugar-sweetened cola, sugar-sweetened sports drinks, sugar-sweetened lemonades/iced teas/juices, artificially-sweetened drinks (e.g., Diet Coke), milk, 100% fruit juice, unsweetened coffee/tea, and bottled water. For the survey data, we will conduct similar linear regression analyses to compare total mean kcals purchased among intervention arms.

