## **Analysis Plan: Preventing non-communicable diseases in Guatemala through sugary drink reduction**

### **Aims:**

The primary aim of this study is to test the association between SSB warning/non-SSB promotion posters compared to control posters and 1) changes in mean fluid ounces of SSBs purchased and 2) changes in total beverage calories purchased by adolescents in school cafeterias in Guatemala City.

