### **Hypotheses:**

Compared to the counterfactual (what would have happened to purchased fluid ounces and total beverage calories if the SSB warning posters had not been implemented, taking into account pre-treatment differences),

- 1) SSB warning/non-SSB promotion posters are associated with greater reduction in mean fluid ounces of SSB purchased
- 2) SSB warning/non-SSB promotion posters are associated with greater reduction in total beverage calories purchased

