### **Primary outcomes:**

1. Fluid ounces of SSBs purchased per sales transaction
  - a. SSBs= any beverage with more than 5g/100mL of sugar reported in the NFP
2. Total beverage calories purchased per sales transaction
  - a. Beverage calories= any calories coming from beverages (SSBs and non-SSBs)

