### **Statistical analysis:**

- Consistency of data: We will conduct analyses to check the consistency of categorical data, including frequency tables and chi-square tests (i.e., purchase type, beverage type, healthfulness perception, label awareness, and demographic variables). To check the consistency of continuous variables, we will create box plots of mean size by beverage categories (SSBs, non-SSBs), purchased quantity, price, volume purchased, serving size, calories, and expenditure.
- Outliers: Within each beverage category (SSBs, non-SSBs), we will examine purchases in the 99th percentile and above (by volume and total calories) to identify any beverage purchases that seem implausible. For the survey data, we will exclude any expenditures that appear implausible.
  - o Data will be pooled (across conditions) when assessing for quality so that we are blind to which condition outliers are in. We will ask the school stores and research assistants to clarify any values that appear out of range prior to excluding any data. Any data that are excluded will be done prior to re-matching data points to their condition.
  - o We will exclude any individual-level data from our customer purchase assessments if no school cafeteria purchase was recorded.
  - o We will exclude any customer purchase assessments if they include implausible purchases (e.g., items not sold at the store). Although we expect to have minimal missing data, we will consider other analytic techniques to handle missing data if the amount is greater than 10%.
- Descriptive analysis: We will summarize (i.e., mean, SE, trends) the primary and secondary outcome variables by condition and time period (pre- or post-). We will also examine changes in primary and secondary variables.
- Statistical design: We will use a difference-in-differences approach to examine the effect of the posters taking into account pre-treatment differences between the treatment and control groups and time trends (pre- and post-). The basic equation for this approach is:

$$Y_{it} = \eta + \gamma d_i + \delta T_t + \alpha d_i * T_t + u_{it}$$

Where  $d_i$  is a binary variable equal to 1 if they were exposed to the poster, 0 otherwise,  $T_t$  is a binary variable equal to 1 in the post period and 0 in the pre period,  $d_i * T_t$  is an interaction term between the two, and  $\alpha$  is the difference-in-differences estimator.

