- The effectiveness of the intervention will be tested by evaluating the null hypothesis that the coefficient of the interaction of time period and intervention is 0, indicating no change in the fluid ounces of SSBs purchased and beverage calories purchased between conditions.
- Regarding the secondary outcomes, we will present the percentage of all transactions and all beverage transactions that include an SSB by condition and time period. To

calculate the total calories per transaction, we will use the Nutrition Facts Panel data of each food or beverage product.

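### With one poster school and one control school, the SAP's primary test cannot separate a poster effect from a change in either school.

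*SAP*

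**What the plan says.** The Protocol (Method for Assigning Subjects to Groups) randomises schools, not students, and plans nine schools over three conditions. Its Analysis Plan handles clustering as follows: "To account for clustering of purchases within schools, test statistics will be corrected using the variance inflation factor (VIF"), with the factor taken from the estimated intraclass correlation.

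The SAP describes a different data set. Sales data come from three schools, and under Description of data: "For our primary analysis, we will look only at the 2 schools which were randomly assigned to condition (one treatment and one control school"). The first primary outcome is "Fluid ounces of SSBs purchased per sales transaction"; the second, beverage calories, is also per transaction. Yet the sales file is introduced thus: "The first is a longitudinal data set (at the school level) of store purchases", with daily purchases.

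Under Statistical analysis: "We will use a difference-in-differences approach to examine the effect of the posters taking into account pre-treatment differences". The equation has an intercept, a group term, a period term, their interaction and one error term. The decision rule is: "The effectiveness of the intervention will be tested by evaluating the null hypothesis that the coefficient of the interaction of time period and intervention" is zero. The Hypotheses open with "Compared to the counterfactual (what would have happened to purchased fluid ounces and total beverage calories" had there been no warning posters.

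The SAP names no standard-error method, no clustering adjustment, and no limitation arising from one school per arm.

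**The concern.** The interaction coefficient is the poster school's change minus the control school's change. Differencing removes stable differences between the schools and shocks common to both. It does not remove a change that happens in one school only. With one school per arm there is no second school in either arm to show how large such changes usually are.

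The test therefore rests on an unstated and uncheckable assumption that, without posters, the two schools would have moved exactly in parallel. If they would not, a precise-looking interval around a school-specific change could be reported as effectiveness on both primary outcomes. More transactions narrow the interval without touching this source of error, so the false-positive rate rises with the amount of data.

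**Working it through.** **Plan's own figure.** The SAP gives no sample size or power for this test. The Protocol (Accrual) gives 82% power for differences of 0.21 SD with 500 students per condition. It reproduces at two-sided alpha 0.05/3 with independent observations: 0.21/√(2/500) = 3.32; 3.32 − 2.39 = 0.93; Φ(0.93) ≈ 82.3%. That figure belongs to the 1,500-student, three-condition design and says nothing about the two-school test.

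**Degrees of freedom (from the documents alone).** 2 schools × 2 periods = 4 cells. The model has 4 coefficients and the design matrix has rank 4. Residual df at school-period level = 4 − 4 = 0.

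**Randomisation p-value (from the documents alone).** Two schools can be allocated one-to-one in 2 ways. The smallest p-value is 1/2 = 0.5 one-sided and 2/2 = 1.0 two-sided.

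**Could the Protocol's VIF repair it?** No. School and arm are the same variable here, so the between-school component cannot be estimated.

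**Could the third school?** It was not randomised and its condition is not stated. If it shared an arm, there would be 6 cells and 5 coefficients (three school levels, period, interaction), leaving 1 df and a critical t of 12.7.

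**Size: assumed inputs.** Two-sided alpha 0.05; ρ = share of transaction variance due to school-by-period shifts; m = transactions per school-period; D = days per period; n = transactions per day; r = correlation of transactions within a day. None is in the documents.

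(a) *Transaction-level test.* Type I error = 2[1 − Φ(1.96/√(1 + (m − 1)ρ))]. For m = 1,000 and ρ = 0.001: √1.999 = 1.414; 1.96/1.414 = 1.386; error 17%.

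| m | ρ = 0.0001 | ρ = 0.001 | ρ = 0.01 |
|---|---|---|---|
| 200 | 5.2% | 7.3% | 26% |
| 1,000 | 6.2% | 17% | 55% |
| 3,000 | 8.6% | 33% | 72% |

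(b) *School-day-level test.* The interval should be wider by w = √(1 + ρ/(r/D + (1 − r)/(Dn))), and type I error = 2[1 − Φ(1.96/w)]. Take r = 0.02 and n = 100. For D = 10 and ρ = 0.001: the denominator is 0.002 + 0.00098 = 0.00298; w = √1.336 = 1.16; error 9.0%.

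| D | ρ = 0.0001 | ρ = 0.001 | ρ = 0.01 |
|---|---|---|---|
| 10 | w 1.02, 5.4% | w 1.16, 9.0% | w 2.09, 35% |
| 20 | w 1.03, 5.8% | w 1.29, 13% | w 2.78, 48% |

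**Does the proposed interval behave?** Simulation: 10,000 replicates, 2 schools × 2 periods × 10 days, unequal daily counts (mean 100, CV 0.4).

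- No drift, r = 0 / 0.01 / 0.02 / 0.05: transaction-level least squares rejects 4.7% / 18.3% / 27.8% / 44.6%. Count-weighted school-day means with an HC2 standard error and a t reference on 36 df reject 4.8% / 5.0% / 4.9% / 5.1%.
- r = 0.02 with ρ = 0.0001 / 0.001 / 0.01: HC2 alone rejects 5.5% / 8.7% / 32.4%. Adding 4ρ × (transaction variance) to the squared standard error gives coverage of 94.9% / 95.1% / 95.6% when ρ is known.
- Lag-1 day autocorrelation of 0.5: HC2 rejects 19.1% (10 days) and 18.8% (20 days). The method does not cure this.

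**Why weight by daily count?** Take no poster effect and 10 days per period, with 100 transactions a day at 5 oz. The exception is two event days in the treated post period, with 250 transactions at 7 oz. Weighted: (800 × 5 + 500 × 7)/1,300 − 5 = 0.77 oz. Unweighted: (8 × 5 + 2 × 7)/10 − 5 = 0.40 oz. Only the weighted form keeps the per-transaction outcome. The example also shows a local event being estimated as an effect.

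**The case against.** The best defence is that difference-in-differences is a recognised design, that these two schools were randomised, and that a test declared conditional on parallel trends is legitimate. The Aims and both hypotheses also speak of association. Declaring the assumption would indeed be an improvement, and the SAP should name it. But the SAP neither states it nor could test it with two schools, and randomising one school to each arm supplies no replication. The association wording does not cancel a stated counterfactual, an effect of the posters and a test of effectiveness.

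Four narrower points stand in part:

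- The Protocol's Analysis Plan puts all outcomes at the purchase level, so table (a) is the likelier reading. Since the SAP leaves its index i undefined and describes school-level daily data, both are shown.
- The sizes run from negligible to severe on assumed inputs. The conclusion therefore rests on the zero degrees of freedom, not on any one entry.
- The remedy does not handle serial correlation. With autocorrelation 0.5 and ρ = 0.001 known, the sensitivity interval covered only about 84% (10 days) and 86% (20 days) in a further simulation. Nor can the data supply the range of ρ.
- With one school per arm, the SAP's trends by condition are already by school. Only the daily resolution would be new. Recorded prices and purchases would allow some checks on price and stock, but the SAP plans none.

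**Conclusion.** The concern holds. The absence of school-level degrees of freedom and the minimum randomisation p-value of 0.5 one-sided follow from the SAP itself. Under either unit of analysis, the planned p-value is valid only if school-by-period variance is zero, which these data cannot show. Over the assumed ranges, the true error of a nominal 5% test runs from 5.2% to 72% by transaction and from 5.4% to 48% by school-day. As written, the SAP permits a statistically significant claim of effectiveness on both primary outcomes that the design cannot support. This should be corrected before the analysis is reported.

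**What to change.** All changes are to the SAP.

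1. **Claim.** Under Statistical analysis, replace the test of effectiveness with the difference-in-differences estimate and an interval described as conditional on these two schools. State the parallel-trends assumption. State also that a poster effect and a school-specific change cannot be separated, and that no p-value is read as evidence of effectiveness. Align the other sections: the Aims *estimate* rather than test; in the Hypotheses, the comparison is with the change in the control school; in the design paragraph, the target is the difference in change between the poster and control school.
2. **Interval.** Define index i. Compute the interval from school-day means weighted by that day's transaction count, with a robust standard error (for example HC2). State that this covers independent day-to-day clustering only, not serial correlation or school-by-period drift.
3. **Sensitivity.** Add an interval with variance = (day-level SE)² + 4ρ × (transaction variance), one term per school-period cell, over a stated and justified range of ρ. Plot the daily series for each school.
4. **Scope.** State that the Protocol's nine-school design and VIF correction do not apply to this analysis.

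The cost is SAP wording and a little programming, with no new data. The downside is wider intervals and a weaker claim.

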### **Statistical analysis:**

- Consistency of data: We will conduct analyses to check the consistency of categorical data, including frequency tables and chi-square tests (i.e., purchase type, beverage type, healthfulness perception, label awareness, and demographic variables). To check the consistency of continuous variables, we will create box plots of mean size by beverage categories (SSBs, non-SSBs), purchased quantity, price, volume purchased, serving size, calories, and expenditure.
- Outliers: Within each beverage category (SSBs, non-SSBs), we will examine purchases in the 99th percentile and above (by volume and total calories) to identify any beverage purchases that seem implausible. For the survey data, we will exclude any expenditures that appear implausible.
  - o Data will be pooled (across conditions) when assessing for quality so that we are blind to which condition outliers are in. We will ask the school stores and research assistants to clarify any values that appear out of range prior to excluding any data. Any data that are excluded will be done prior to re-matching data points to their condition.
  - o We will exclude any individual-level data from our customer purchase assessments if no school cafeteria purchase was recorded.
  - o We will exclude any customer purchase assessments if they include implausible purchases (e.g., items not sold at the store). Although we expect to have minimal missing data, we will consider other analytic techniques to handle missing data if the amount is greater than 10%.
- Descriptive analysis: We will summarize (i.e., mean, SE, trends) the primary and secondary outcome variables by condition and time period (pre- or post-). We will also examine changes in primary and secondary variables.
- Statistical design: We will use a difference-in-differences approach to examine the effect of the posters taking into account pre-treatment differences between the treatment and control groups and time trends (pre- and post-). The basic equation for this approach is:

$$Y_{it} = \eta + \gamma d_i + \delta T_t + \alpha d_i * T_t + u_{it}$$

Where  $d_i$  is a binary variable equal to 1 if they were exposed to the poster, 0 otherwise,  $T_t$  is a binary variable equal to 1 in the post period and 0 in the pre period,  $d_i * T_t$  is an interaction term between the two, and  $\alpha$  is the difference-in-differences estimator.

- The effectiveness of the intervention will be tested by evaluating the null hypothesis that the coefficient of the interaction of time period and intervention is 0, indicating no change in the fluid ounces of SSBs purchased and beverage calories purchased between conditions.
- Regarding the secondary outcomes, we will present the percentage of all transactions and all beverage transactions that include an SSB by condition and time period. To

calculate the total calories per transaction, we will use the Nutrition Facts Panel data of each food or beverage product.

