Students and their caregivers will first be contacted about study participation using a permission letter (see Appendix A) sent either as a printed letter or electronically. The letter will explain that their children may be asked to complete a short survey after making a purchase at the school store. Caregivers who wish to refuse participation can call a number provided in the permission letter. A list will be maintained with the names of students who have permission to participate. Research assistants will consult this list before administering any surveys to ensure the student has permission to participate. Adolescents who consent to participate and have made a purchase from the school store will be given the opportunity to complete a short survey; verbal assent must be obtained prior to enrollment. Research assistants will be stationed at the school stores during the heaviest traffic times (between 10:00am and 1:30pm and 2:30pm and 3:30pm) Monday to Friday and will invite adolescents to participate in the survey after they make a food and/or beverage purchase at the school store. Research assistants will record the item purchased (type of food/beverage) along with brand, quantity, size, and price. In addition, we will administer a survey that includes a validated beverage frequency questionnaire to assess typical beverage intake (Appendix B). Research assistants will also record the number of students who refuse participation along with their gender. The survey is estimated to last approximately 5-10 minutes. Participants will only be eligible to take the survey once.

Data Management

Describe how and who manages confidential data, including how and where it will be stored and analyzed. For instance, describe if paper or electronic report forms will be used, how corrections to the report form will be made, how data will be entered into any database, and the person(s) responsible for creating and maintaining the research database. Describe the use of pseudonyms, code numbers and how listing of such identifiers will be kept separate from the research data.

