The objective of this study is to conduct one of the first field experiments to assess the degree to which sugary drink warning labels encourage adolescents to reduce their intake in a country that does not yet have any front-of-package food labeling regulations. We will also evaluate whether a graphic-based warning label is more effective compared to a text-based warning label.

Primary outcome variable(s)

The primary outcome will be mean ounces of sugary beverages purchased based on sales data, which will include the date of the transaction and the type of food or beverage sold (e.g., diet soda, lemonade) along with the item brand, size, quantity, and price.

Secondary outcome variable(s)

Our secondary outcomes will be the total kilocalories (kcal) purchased at the school store based on the surveys we collect. A measure of total calories purchased will allow us to assess whether adolescents who buy fewer sugary drinks compensate by buying other snack foods. We define a sugary drink as any non-alcoholic beverage that lists any form of caloric sugar-based sweetener as an ingredient (this would not include 100% juice). We will also record the presence and type of food/beverage marketing in the store.

Background

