have shopped at one of the participating stores will qualify to participate. We will use the communication channel each school prefers (e.g., e-mail, printed letters sent home with students) to send permission letters to caregivers (see Appendix A). The letters will explain that their children may be asked to complete a short survey after making a purchase at the school store. Caregivers who wish to refuse participation can call a number provided in the permission letter. All students whose caregivers did not withdraw will be eligible to participate in the survey. Permission letters will be sent two weeks before data collection. Adolescents who have made a purchase from the school store will be asked if they want to complete a short survey; verbal assent must be obtained prior to enrollment (see Appendix C for oral consent script). School Store Setting: Nine schools will be participating in this research and randomization will be stratified based on whether a school is public (n = 6) or private (n = 3). The Penn research team will use a random number generator to randomize schools and the Guatemala team will implement the labels based on the randomization assignment. Each pair of matched private/public schools will be randomized to 1 of 3 labeling conditions: 1) calorie label (control); 2) text warning labels; or 3) graphic warning labels displaying amounts of sugar (see Appendix F). The warning label language will be translated into Spanish before the labels are implemented in the school stores. In this six-week study, we will receive purchasing data from the schools during two weeks without labels, two weeks when labels are displayed, and two weeks after labels have been removed. Warning Label Survey: During the intervention weeks, we will survey approximately 1500 adolescents after they have made a purchase at the school store. We will stratify recruitment to ensure approximately half of the 1500 surveyed students (n=750) are enrolled in public school and half (n=750) are enrolled in private school. Adolescents will be asked if they want to participate in a short, 5-10 minute survey. They will be offered a small prize (e.g., school supplies like pens or pencils) as a token of appreciation. The survey will include constructs that map onto our conceptual model of label effects, such as nutritional knowledge, label awareness, and trust of information on nutritional labels (see Appendix B for survey questions). We will also administer a beverage intake questionnaire (see Appendix D). This questionnaire has been validated among children and adolescents (42,43) Demographic Information: During the survey, we will ask participants to provide basic demographic information including age, sex, race/ethnicity, grade level, and height and weight (see Appendix B for demographic questions). Sales Data: We will collect sales data by setting up a point of sale system in each school store. This system will allow us to collect sales data from each store that will include a row for each purchase made at the school store, including the date of the transaction and the type of food or beverage sold (e.g., diet soda, lemonade) along with the item brand, size, quantity, and price. We will also record the presence and type of food/beverage marketing in the store.

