
Study duration

We anticipate it will take the entirety of the six week data collection period to survey all 1500 adolescents. It will take 5-10 minutes for each participant to complete the survey. We aim to implement the warning labels in school stores by May 2018 and will complete the data collection by the end of June 2018.

Resources necessary for human research protection

Describe research staff and justify that the staff are adequate in number and qualifications to conduct the research. Describe how you will ensure that all staff assisting with the research are adequately informed about the protocol and their research related duties. Please allow adequate time for the researchers to conduct and complete the research. Please confirm that there are adequate facilities for the research.

Characteristics of the Study Population

Target population

To be eligible for the survey component of this project, participants must be: 1) Between 12-18 years or older; 2) Be a currently enrolled student at one of the enrolled schools 3) Have made a purchase at the school store.

Subjects enrolled by Penn Researchers

0

Subjects enrolled by Collaborating Researchers

1500

Accrual

The schools participating in this study will enable us to easily recruit students shopping at the school stores. With a sample size of 1500 (500 per labeling condition), this study is powered to detect small mean differences between the conditions. Specifically, if all three conditions differ by only .21 standard deviations, there is an 82% chance that we would find all differences to be significant.

Key inclusion criteria

To be eligible for the survey component of this project, participants must be: 1) Between 12-18 years or older; 2) Be a currently enrolled student at one of the enrolled schools 3) Have made a purchase at the school store.

Key exclusion criteria

Individuals not meeting the inclusion criteria above will be excluded. Those who will not or cannot give assent will also be excluded from the study. No one will be excluded on the basis of sex or race

Vulnerable Populations

Children Form

Pregnant women (if the study procedures may affect the condition of the pregnant woman or fetus) Form

Fetuses and/or Neonates Form

Prisoners Form

Other

None of the above populations are included in the research study

The following documents are currently attached to this item:

Vulnerable Populations (inclusionofchildren.doc)

Populations vulnerable to undue influence or coercion

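### The protocol gives two survey windows: one undercuts its 82% power figure, the other leaves the SAP's pre/post survey reporting without baseline data

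*SAP*

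**What the plan says.** The protocol's Design section divides the six weeks into an unlabelled fortnight, a labelled fortnight and a fortnight after removal. It then says: "During the intervention weeks, we will survey approximately 1500 adolescents after they have made a purchase at the school store". Under Study duration the protocol expects that "it will take the entirety of the six week data collection period to survey all 1500 adolescents". Under Administration of Surveys and/or Process, "Participants will only be eligible to take the survey once", so respondents in different phases are different students.

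The only power statement in either document is under Accrual. With 1,500 students, 500 per labelling condition, "if all three conditions differ by only .21 standard deviations, there is an 82% chance that we would find all differences to be significant".

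The survey carries the protocol's secondary outcome: "Our secondary outcomes will be the total kilocalories (kcal) purchased at the school store based on the surveys we collect". The Analysis Plan says: "For the survey data, we will conduct similar linear regression analyses to compare total mean kcals purchased among intervention arms". The sales model to which these regressions are similar contains arm, period and their interaction, but the survey sentence names only arms.

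All three SAP secondary outcomes come from the survey. Its Statistical analysis section will summarise "the primary and secondary outcome variables by condition and time period (pre- or post", and later commits to presenting the percentage of "all transactions and all beverage transactions that include an SSB by condition and time period". The SAP's Description of data dates the sales records (July to August 2019) but not the survey. It restricts the primary analysis to one treatment and one control school.

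**The concern.** The two windows lead to different data sets. Confining surveys to label weeks puts every respondent under a label and leaves no one surveyed at baseline. Spreading them over six weeks supplies baseline respondents but leaves far fewer than 500 per condition under labels. The power statement relies on the first arrangement and the SAP's by-period tables on the second. As written, either a stated figure or a stated analysis fails.

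What is at stake is the protocol's secondary outcome and every secondary outcome in the SAP. There is also a risk in the analysis itself. If surveys run through all six weeks and the regression compares arms only, students who saw no label are counted as evidence on the label effect.

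**Working it through.** **Inputs from the protocol.** 1,500 students, 500 per condition, spacing 0.21 SD, stated power 82% (Accrual); three two-week phases (Design); three pairwise comparisons with a Holm correction (Analysis Plan).

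**Assumptions, because the documents do not give them.** Two-sided 5%, unit SD, independent students (no clustering), surveys spread evenly over the weeks if they span all six, and condition means 0, 0.21 and 0.42 SD.

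**Step 1: reproduce the 82%.** For one pair, SE = √(2/500) = 0.0632, and 0.21/0.0632 = 3.32.
- At 5%: Φ(3.32 − 1.96) = 91.3%.
- At 0.05/3: Φ(3.32 − 2.39) = 82.3%.
- All three differences significant, by simulation (1,000,000 normal draws): 82.6% unadjusted, 82.5% under Holm.

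The stated figure is therefore reproduced, but only with 500 against 500 in a single between-condition contrast at the full 0.21 SD. That means every survey under labels.

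**Step 2: six-week window, label weeks analysed.** 500/3 ≈ 167 per condition. SE = √(2/167) = 0.1094; 0.21/0.1094 = 1.92; Φ(1.92 − 1.96) = 48.4% for one pair.

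**Step 3: six-week window, all weeks pooled in an arm-only comparison.** If the effect occurs only while labels are up, the average difference is 0.21 × 2/6 = 0.07 SD. With SE 0.0632, 0.07/0.0632 = 1.11 and Φ(1.11 − 1.96) = 19.7%. If the effect persists in full after removal, the average is 0.21 × 4/6 = 0.14 SD, giving 60.0%.

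**Step 4: six-week window, arm-by-period contrast (labelled against baseline).** SE = √(4/166.7) = 0.1549; 0.21/0.1549 = 1.36; Φ(1.36 − 1.96) = 27.3%.

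| Survey window and contrast | Surveys per condition used | Spacing (SD) | One pair, 5% | All three, Holm |
|---|---|---|---|---|
| Label weeks only | 500 | 0.21 | 91.3% | 82.5% |
| Six weeks, label weeks analysed | 167 | 0.21 | 48.4% | 13.7% |
| Six weeks pooled, effect only in label weeks | 500 | 0.07 | 19.7% | 0.6% |
| Six weeks pooled, effect persists after removal | 500 | 0.14 | 60.0% | 27.0% |
| Six weeks, arm by period | 167 + 167 | 0.21 | 27.3% | 1.9% |

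**Step 5: the SAP's tables.** With a label-weeks window the number of pre-period surveys is zero in each condition, so the pre column of every survey table is empty. With the six-week window the column can be filled.

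**The case against.** The strongest reply is that the 82% and the SAP belong to different designs. The power statement is for nine schools and three label arms. The SAP concerns posters, three schools, and a primary analysis of two of them, and it claims no power. That is correct. The percentages above apply to the protocol's design only and say nothing about the power of any SAP analysis. The conflict between the two protocol sections remains, as does the SAP's need for baseline surveys.

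It can also be said that the survey regression compares arms only, so label weeks, 500 per condition and that regression agree, leaving one forecast under Study duration as the outlier. That may be what was intended. But then the SAP's pre/post survey tables cannot be produced. Reading the intervention weeks loosely as all six is hard to sustain, because Design has just separated the labelled fortnight from the others. The 82% could survive a six-week window if 0.21 SD were a six-week average, but that average would include weeks before any label was shown.

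Three stronger inferences are tempting, and the documents do not support them.
- *That the SAP tests a survey period contrast.* Its by-period survey reporting is descriptive, and its null hypothesis names only fluid ounces and beverage calories, which are the sales outcomes.
- *That a by-period survey contrast must be less precise in the SAP's two schools, as it is for independent students.* With one school per condition, a label-weeks comparison carries the whole between-school variance, while a by-period contrast cancels its stable part. Take, for illustration, 500 surveys per condition split evenly over two periods, and an ICC of 0.01 with a stable school effect. The label-weeks SE is √(2[0.01 + 0.99/500]) = 0.155, against √(8 × 0.99/500) = 0.126 by period. The order reverses, and the documents give no ICC.
- *That the SAP's sales coefficient is diluted by weeks after removal.* The SAP names only a pre and a post period and never mentions removal. The simplest reading is that removal was dropped, and the binary term is then adequate. Dating the two periods is a minor clarification.

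**Conclusion.** The concern holds in limited form. The protocol contradicts itself on the survey weeks, and neither window satisfies both the 82% and the SAP's by-period survey reporting. With the six-week window and an even spread, power for all three differences falls from about 82% to about 14% when label weeks are analysed, and to under 1% if unlabelled weeks are pooled and the effect does not outlast the labels. These figures rest on the even spread, two-sided 5% and independent students; within-school correlation would lower them all. With the label-weeks window, the 82% stands before clustering, but the SAP's survey results have no baseline. If they use the same two schools as the primary analysis, a survey difference could not be separated from a pre-existing difference between those schools.

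This should be corrected. It affects secondary outcomes, not the primary sales analysis.

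**What to change.** Reconcile Design and Study duration to one survey window, and state in the SAP which survey weeks enter each survey outcome.

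- **If surveys span phases:** include period and arm-by-period in the survey regression, and do not pool unlabelled weeks into the arm comparison. Restate the 82% for the number per condition actually surveyed under labels. Label it as a figure for the protocol's three-arm design that does not apply to the SAP's two-school analysis.
- **If surveys are in label weeks only:** remove the pre/post reporting of survey outcomes from the SAP's Statistical analysis section, and state that the survey comparison has no baseline.

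As a minor clarification, date the sales pre and post periods.

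The cost is a few sentences and, in the first case, a period term and its interaction with arm. The stated power becomes less favourable: at protocol size and before clustering, 48% for one pair in label weeks, or 27% for one pair as an arm-by-period contrast. Survey results should then be described as supportive. If no baseline surveys were taken, no rewording can supply them.
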